#### **Design**

A randomized controlled trial will be conducted. The 2 potential groups to which patients may be randomized are: 1) a simple telehealth intervention that utilizes the Way to Health Platform to send SMS messages directly, and 2) standard of care. Given that assignment to the interventions will be obvious to the participants, study staff and investigators, no blinding procedures will be employed. Of note, any participant randomized to the usual care arm will be offered 90 days of telehealth monitoring after study completion.

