#### **Study duration**

The estimated length of the study will be approximately one year. Each participant will be enrolled for a period of 90 days. The period of follow up will begin on the discharge day and end exactly 90 days from that date. Once patients have completed the 90 days of observation, they are not permitted to be re-enrolled in the study. If a control patient chooses to receive telehealth text messages after the 90 days, they will be in the study for up to 180 days.

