**Analysis Plan**

The primary analysis will include a comparison of the demographics and clinical data for the intervention group and the usual care group. To determine if there is a difference in the rates of readmission between the groups, univariable logistic regression analysis will be performed. Any predictors which were different between the groups will be used for adjustment in a multivariable logistic regression. We plan to analyze the data at the 6 month mark. If a significant difference is found, given the low cost of the intervention and potential benefits, the study will be stopped and all patients admitted to the hepatology service will be eligible for telehealth monitoring. Data for the secondary outcomes including changes in quality of life and patient satisfaction will be explored.

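### The 6-month stopping rule names no direction, so read literally a significant excess of readmissions on telehealth leads to the same action as a significant reduction

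*Protocol*

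**What the plan says.** The Analysis Plan in the protocol describes the comparison without a direction: "To determine if there is a difference in the rates of readmission between the groups, univariable logistic regression analysis will be performed". It then sets an interim look, "We plan to analyze the data at the 6 month mark", and a binding consequence: "If a significant difference is found, given the low cost of the intervention and potential benefits, the study will be stopped and all patients admitted". The closing part of that sentence, given in full, is that "all patients admitted to the hepatology service will be eligible for telehealth monitoring". No other outcome of the look is given an action.

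Five other places bear on how to read this:

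- **Primary outcome variable(s)** is worded in one direction, as a reduction in readmissions.
- **Design** states that nobody is blinded, and that "any participant randomized to the usual care arm will be offered 90 days of telehealth monitoring after study completion".
- **Data and Safety Monitoring** gives monitoring to the principal investigator and co-investigator, sends adverse events to the IRB, and says a DSMB is not yet needed.
- **DMC or DSMB exists**, in the continuing review form, is answered No.
- **Potential Study Risks** and **Risk / Benefit Assessment** rate the risk as minimal. Neither discusses an excess of readmissions.

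**The concern.** A stopping rule has a trigger and an action, and the two should match. Here the trigger covers a difference either way, while the action makes sense only if telehealth is better. Someone applying the sentence exactly would make telehealth available to all hepatology admissions after seeing it significantly raise readmissions.

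This is the only stopping rule in the document. An excess of readmissions is the study's main outcome going the wrong way, and the protocol does not say that it would be handled as an adverse event. The people who see the interim result are the unblinded investigators, and no independent committee reads it with them. That is the setting in which a rule should leave least to interpretation.

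The point concerns direction and consequence only. It does not concern the significance level, the timing of the look or the amount of follow-up available by then.

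**Working it through.** **Step 1: the text, element by element.**

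| Element | Where | Direction stated? |
|---|---|---|
| Hypothesis tested | Analysis Plan | No: a difference between groups |
| Interim trigger | Analysis Plan | No: a significant difference |
| Rationale for acting | Analysis Plan | Implied: low cost and possible benefit |
| Primary outcome | Primary outcome variable(s) | Yes: a decrease |
| Action if telehealth is better | Analysis Plan | Stop; hepatology admissions become eligible |
| Action if telehealth is worse | Nowhere | None separate from the line above |

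The rationale and the primary outcome point to benefit, but neither is written as a condition on the trigger. The defect follows from this table alone and needs no arithmetic.

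**Step 2: inputs for an illustration of size.** From the document:

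- about 426 patients (Abstract);
- 1:1 allocation (Method for Assigning Subjects to Groups);
- a 30-day readmission rate of 28% at the site (Background);
- a look at 6 months (Analysis Plan);
- duration: "The estimated length of the study will be approximately one year" (Study duration).

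Assumed, because the document does not give them: a two-sided 0.05 test at the look, even accrual over 9 to 12 months, and the size of any true harm. The 426 itself cannot be reproduced, because significance level, power, target effect and dropout are not stated. Nothing here depends on reproducing it.

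**Step 3: evaluable patients at month 6.** With even accrual, patients enrolled in the first 5 of 6 months have 30 days of follow-up.

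- 12-month accrual: 426 × 6/12 = 213 enrolled; 213 × 5/6 ÷ 2 ≈ 89 per arm.
- 9-month accrual: 426 × 6/9 = 284 enrolled; 284 × 5/6 ÷ 2 ≈ 118 per arm.

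**Step 4: chance of a trigger in the harm direction.** This uses a pooled two-proportion z-test with normal approximation, n per arm, control rate p_c and telehealth rate p_t:

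P(harm trigger) = 1 − Φ{[1.96·s0 − (p_t − p_c)] / s1}

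where p̄ = (p_c + p_t)/2, s0 = √[2p̄(1 − p̄)/n] and s1 = √[(p_c(1 − p_c) + p_t(1 − p_t))/n].

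Example with n = 89 and 28% against 38%: p̄ = 0.33, s0 = 0.0705, s1 = 0.0701. Then (1.96 × 0.0705 − 0.10)/0.0701 = 0.54, and 1 − Φ(0.54) ≈ 0.29.

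| True telehealth rate | n = 89 per arm | n = 118 per arm |
|---|---|---|
| 28% (no effect) | 0.025 | 0.025 |
| 33% (+5 points) | 0.11 | 0.13 |
| 38% (+10 points) | 0.29 | 0.37 |

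**Step 5: sensitivity.** With 60 to 106 evaluable per arm, a 5-point rise from 28% gives about 8.6–12.1% and a 10-point rise about 21–34%. Starting instead from the 53% consortium 90-day rate in Background, the figures are about 7.9–11.0% and 20–31%. The order of magnitude does not change.

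**The case against.** The best reply is that the sentence limits itself. Its reason for acting is low cost and possible benefit, which makes sense only for a result in favour of telehealth. The primary outcome is a decrease, and Potential Study Benefits describes a reduced need for readmission. On that reading the trigger is a significant decrease. Sidedness is also something a protocol may leave to a statistical analysis plan, and the investigators do monitor data and report adverse events to the IRB.

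Much of this stands. Benefit was probably meant, and the fault is one of drafting. But possible benefit is offered as a reason for acting on a difference, not as a requirement that the difference be favourable. If benefit-only is accepted as the meaning, the rule still has no response to the opposite result. Nor is this detail left for later: the protocol itself fixes both trigger and consequence.

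Four stronger readings are tempting, and the documents do not support them:

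- **That the protocol orders a roll-out of a harmful programme.** The text says patients become eligible, which is permissive, and nothing suggests the investigators would extend telehealth after seeing harm.
- **That usual-care patients would still be offered telehealth whatever the interim data show.** The offer is stated, but its fate after an adverse look is not addressed. That reading is drawn from silence.
- **That telehealth is likely to raise readmissions.** Closer surveillance and changes to medication outside a visit are described under Study Instruments and Risk / Benefit Assessment, but neither section says they increase admissions.
- **That the rule would probably fire under harm.** At true telehealth rates of 40% or 45% the probability is about 0.39–0.49 or 0.66–0.78. Those are 12- and 17-point rises with no basis in the document.

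**Conclusion.** The rule is wrong as written, and the remedy is a wording correction. The protocol states a trigger without direction and one action suited to only one direction. It gives no response to a significantly adverse interim result. The context shows that benefit was the likely intent, which limits the seriousness but leaves the sentence incorrect.

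The conclusion rests on the text. The probabilities (about 2.5% with no true effect, 11–13% for a 5-point rise, 29–37% for a 10-point rise) only illustrate size. They depend on an assumed two-sided 0.05 test, even accrual over 9 to 12 months, 30-day outcomes and a 28% control rate. The document gives no reason to expect a rise of either size.

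**What to change.** In the Analysis Plan, reword the stopping sentence so that early stopping with extension of telehealth applies only if the readmission rate is significantly lower in the telehealth arm. Add a sentence there or under Data and Safety Monitoring, agreed in advance by the investigators and the IRB, saying what the study does and who is told if the rate is higher in that arm. The content of that response is for them to decide.

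The cost is one or two sentences in a protocol amendment, with no additional patients, data or analyses.

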**The following documents are currently attached to this item:**

*There are no documents attached for this item.*

Are you conducting research outside of the United States?

No

**Data confidentiality**

**x Paper-based records will be kept in a secure location and only be accessible to personnel involved in the study.**

**x Computer-based files will only be made available to personnel involved in the study through the use of access privileges and passwords.**

**Prior to access to any study-related information, personnel will be required to sign statements agreeing to protect the security and confidentiality of identifiable information.**

**x Wherever feasible, identifiers will be removed from study-related information.**

**A Certificate of Confidentiality will be obtained, because the research could place the subject at risk of criminal or civil liability or cause damage to the subject's financial standing, employability, or liability.**

**A waiver of documentation of consent is being requested, because the only link between the subject and the study would be the consent document and the primary risk is a breach of confidentiality. (This is not an option for FDA-regulated research.)**

**Precautions are in place to ensure the data is secure by using passwords and encryption, because the research involves web-based surveys.**

**Audio and/or video recordings will be transcribed and then destroyed to eliminate audible identification of subjects.**

**Subject Confidentiality**

Confidential information about all enrolled subjects will be secured on the Way to Health Platform. Only necessary study staff will have access to such data. Additionally, only data in a de-identified form will be available for statistical analyses. All study staff will have password protected access to Way to Health. Though we do not expect any breaches of confidentiality, if they do occur they will be reported directly to the IRB within 24 hours of after discovery. Paper-based records will be kept in a secure location in locked file cabinets and only be accessible to personnel involved in the study.

**Sensitive Research Information\***

Does this research involve collection of sensitive information about the subjects that should be excluded from the electronic medical record?

No

**Subject Privacy**

Privacy refers to the person's desire to control access of others to themselves. Privacy concerns people, whereas confidentiality concerns data. Describe the strategies to protect privacy giving consideration to

the following: The degree to which privacy can be expected in the proposed research and the safeguards that will be put into place to respect those boundaries. The methods used to identify and contact potential participants. The settings in which an individual will be interacting with an investigator. The privacy guidelines developed by relevant professions, professional associations and scholarly disciplines (e.g., psychiatry, genetic counseling, oral history, anthropology, psychology).

Patients seen in the hospital with a referring clinician will be given the opportunity to obtain further information if they choose. Participants will be told that they do not have to answer any questions if they do not wish and can drop out of the study at any time, without affecting their medical care or the cost of their care. They will be told that they may or may not benefit directly from the study and that all information will be kept strictly confidential, except as required by law. Subjects will be given a copy of the consent document. All efforts will be made by study staff to ensure subject privacy. Subjects will only be seen by the PI and members of the research team in the privacy of their hospital room and will not be identified to anyone in clinic practice as anything other than a regular patient.

**Data Disclosure**

Will the data be disclosed to anyone who is not listed under Personnel?

No data will be disclosed to anyone not listed under the personnel section of this protocol.

**Data Protection\***

- Name
- Street address, city, county, precinct, zip code, and equivalent geocodes
- All elements of dates (except year) for dates directly related to an individual and all ages over 89
- Telephone and fax number
- Electronic mail addresses
- Social security numbers
- Medical record numbers
- Health plan ID numbers
- Account numbers
- Certificate/license numbers
- Vehicle identifiers and serial numbers, including license plate numbers
- Device identifiers/serial numbers
- Web addresses (URLs)
- Internet IP addresses
- Biometric identifiers, incl. finger and voice prints
- Full face photographic images and any comparable images
- Any other unique identifying number, characteristic, or code
- None

Does your research request both a waiver of HIPAA authorization for collection of patient information and involve providing Protected Health Information ("PHI") that is classified as a "limited data set" (city/town/state/zip code, dates except year, ages less than 90 or aggregate report for over 90) to a recipient outside of the University of Pennsylvania covered entity?

No

**Tissue Specimens Obtained as Part of Research\***

Are Tissue Specimens being obtained for research?

No

**Tissue Specimens - Collected during regular care\***

Will tissue specimens be collected during regular clinical care (for treatment or diagnosis)?

No

**Tissue Specimens - otherwise discarded\***

Would specimens otherwise be discarded?

No

**Tissue Specimens - publicly available\***

Will tissue specimens be publicly available?

No

**Tissue Specimens - Collected as part of research protocol\***

Will tissue specimens be collected as part of the research protocol?

No

**Tissue Specimens - Banking of blood, tissue etc. for future use\***

Does research involve banking of blood, tissue, etc. for future use?

No

**Genetic testing**

If genetic testing is involved, describe the nature of the tests, including if the testing is predicative or exploratory in nature. If predictive, please describe plan for disclosing results to subjects and provision of genetic counseling. Describe how subject confidentiality will be protected Note: If no genetic testing is to be obtained, write: "Not applicable."

Not applicable

## **Consent**

### ***1. Consent Process***

#### **Overview**

Study recruitment will be accomplished primarily by personal interviews conducted by the PI or study staff prior to the date of discharge from an inpatient hospitalization on the Hepatology service at the University of Pennsylvania. Some patients may be enrolled and consented over the telephone. Any patient who consents over the phone, will be given a copy of the in-person consent form by mail or email. Potential study subjects will be informed of the criteria for study inclusion, data to be collected during the period of observation, as well as the risks and potential benefits of study enrollment. This information will be provided in the body of the consent form as well as presented verbally to the study participant during the informed consent process. Consent will be documented by the signature of the participant and will be witnessed by clinical personnel not affiliated with the study. A copy of the signed consent will then be provided to the participant for their records. For those potential participants who are overwhelmed, fail to consent for study inclusion but agree to be approached after discharge, we will attempt a telephone consent within one week of hospital discharge. A proportion of eligible patients may be exhibiting significant cognitive impairment and the lack of capacity to provide consent. As such, all patients will require surrogate consent by a legally authorized representative. The investigator or staff will determine the appropriate family member-person to contact regarding the study, based on the standard operating procedures of the facility and local and state laws.

#### **Children and Adolescents**

Not applicable

#### **Adult Subjects Not Competent to Give Consent**

Subjects may have Hepatic Encephalopathy or altered mental status and may not be able to give informed consent. In situations when a patient is unable to provide consent, in these cases consent will be obtained from a legally authorized representative as identified by the attending physician/medical team. The patient ability to consent will be re-evaluated within one week of hospital discharge.

### ***2. Waiver of Consent***

#### **Waiver or Alteration of Informed Consent\***

No Waiver Requested

**Minimal Risk\***

**Impact on Subject Rights and Welfare\***

**Waiver Essential to Research\***

**Additional Information to Subjects**

**Written Statement of Research\***

No

**If no written statement will be provided, please provide justification**

**The following documents are currently attached to this item:**

*There are no documents attached for this item.*

**Risk / Benefit**

**Potential Study Risks**

Study inclusion poses no more than minimal risk to the participant enrolled. There should be no adverse events associated with the collection of vital signs, medication administration records, or symptom logs. Patients and caregivers will have clear instructions as to how to reach the team in the event that it is after hours. This intervention results in no more than minimal risk as compared to that which would be incurred in the context of routine follow up care of a cirrhotic patient. Another potential risk of this study is a breach of participant confidentiality. We will minimize this risk by linking individual identifying information with participant ID numbers only in one single secure file that will only be accessed by the study team in the case of an adverse medical event, participant dropout, or if otherwise deemed necessary by the Principal Investigator. All other identifying information will be discarded after initial contact with the Study Coordinator.

**Potential Study Benefits**

The study can impact those enrolled in the intervention arm by decreasing their need for hospital readmission and by having a more rapid means for their liver disease symptoms to be addressed. Furthermore, data obtained will allow for identification of factors associated with readmissions in cirrhotic patients and an opportunity to address these factors in the future through refinement of the intervention. Given that the usual care arm is also offered 90 days of telehealth monitoring at the end of the study, both groups reap the potential benefit of the intervention.

**Alternatives to Participation (optional)**

Participation is voluntary and optional.

**Data and Safety Monitoring**

Data will be monitored by the PI and Co-investigator. Any adverse events will be reported to the IRB. As this is currently a single site trial, we do not yet need a DSMB.

**The following documents are currently attached to this item:**

*There are no documents attached for this item.*

**Risk / Benefit Assessment**

Given that the study poses no more than minimal risk to the subject enrolled and there are no adverse effects associated with the collection of vital signs, medication administration records, or symptom logs, there are large potential benefits to enrollment that far outweigh the risks. These benefits include rapid identification of clinical deterioration, an opportunity to adjust medications outside of an office visit and in the context of clinical data points, and to refine an intervention to improve readmission rates and quality of life in cirrhotic patients.

## General Attachments

The following documents are currently attached to this item:

*There are no documents attached for this item.*
